- Part 2 is a Phase 3, 52-week, open-label, randomized, multinational, clinical study evaluating the efficacy and safety of AFREZZA (insulin human) inhalation powder in combination with a basal insulin versus insulin aspart in combination with a basal insulin in pediatric subjects with type 1 or type 2 diabetes mellitus. The design of the Phase 3 study may be modified based on the results from Part 1. Design for the Phase 3 study is in development (Section 18.3 - Appendix C).

STUDY NUMBER	MKC-TI-155 Part 1
COMPOUND:	AFREZZA® (insulin human) Inhalation Powder
STUDY TITLE	Open-label, single-arm, multiple-dose safety, titration, and pharmacokinetic study of AFREZZA® in pediatric subjects ages 4 to 17 years with type 1 diabetes mellitus
INVESTIGATOR/STUDY LOCATION	United States
PHASE OF DEVELOPMENT	2
STUDY OBJECTIVES	
 Assess the safety and tolerability of AFREZZA in children ages 4 to 17 years with T1DM Assess PK following a prandial dose of AFREZZA in children ages 4 to 17 years with T1DM Assess the ability to titrate the prandial and supplemental dose of AFREZZA at each meal using postprandial self-monitored blood glucose values obtained 120 to 150 minutes after each prandial dose of AFREZZA in children ages 4 to 17 years with T1DM
STUDY DESIGN	
Part 1 of the study will be a single-arm, multi-center, open-label, uncontrolled study to evaluate PK, safety, and ability to titrate AFREZZA® in children ages 4 to 17 years with T1DM, who were previously on a regimen of basal-bolus insulin therapy administered by multiple daily injections (MDI).
 
On Day 1, subjects will receive a single dose of AFREZZA prior to PK sampling. There will be 3 different doses of AFREZZA for the PK study. The AFREZZA® dose (4, 8, or 12 units) will be based on the dose of subcutaneous (SC) rapid-acting analog (RAA) that the subject would usually receive with breakfast. During the 4-week titration period following the PK visit, each subject will be titrated with AFREZZA according to the titration

	
rules given.
 
The study will be conducted sequentially in age cohorts beginning with Cohort 1 and then proceeding to Cohort 2 and Cohort 3 in parallel. Approximately 46 subjects will be enrolled into 3 age cohorts:
 
Cohort 1: 13 to 17 years; approximately 18 subjects distributed across 4, 8, and 12 unit starting dose groups. Before proceeding to Cohort 2 and Cohort 3, at least 14 subjects must be dosed (complete PK Visit 2). Of those, at least 6 subjects must receive at least the 8 unit dose.
 
Cohort 2: 8 to 12 years; approximately 14 subjects distributed across 4, 8, and 12 unit starting dose groups, as derived from the insulin:carb ratio – Figure 1 (the sample size may be adapted after taking the PK data from Cohort 1 into account)..
 
Cohort 3: 4 to 7 years; approximately 14 subjects will be treated and assessed for AFREZZA with a starting dose of distributed across 4, 8, and 12 unit starting dose groups, as derived from the insulin:carb ratio – Figure 1. The sample size may be adapted after evaluating the PK data from Cohort 1 and Cohort 2.
 
The study consists of:
 
 • Up to 3-week screening period • PK assessment period: 1 day, after a single dose of AFREZZA® • Dose titration period: approximately a 4-week period with multiple doses of AFREZZA • A follow-up visit will occur approximately 1 week after the end of AFREZZA treatment for safety assessments (duration 1 day) 
Stopping rules
 
 • Administration of AFREZZA in any dose group(s) of an age cohort may be halted if the Sponsor or data safety monitoring committee (DMC) considers a dose group or age cohort to be unsafe or that it is unreasonable to continue. • The study may also be stopped if the Sponsor or DMC considers it not appropriate to proceed to the next age cohorts based on safety, PK, or titration data.
STUDY POPULATION	
Main selection criteria	
Inclusion criteria
 
 1. Written consent or oral assent from the pediatric subject and

	
written informed consent from the parent(s) or legal guardian and a witness, as required by both state and federal laws and the local Institutional Review Board;
 
2. Children aged ≥ 4 and ≤ 17 years (enrolled into 3 age cohorts: 13 to 17, 8 to 12, and 4 to 7 years);
 
3. Clinical diagnosis of T1DM and using insulin for at least 1 year;
 
4. Currently receiving a regimen of basal/bolus insulin administered by MDI for at least 6 weeks prior to enrollment;
 
5. Subjects with pre-breakfast self-monitored blood glucose values between 80 and 250 mg/dL for 5 of 7 documented daily readings obtained in the week prior to Visit 2 (readings to be taken using glucometer provided at Screening Visit 1) and reported via the e-Diary;
 
6. Subjects on a regimen of insulin via continuous SC insulin infusion may be enrolled if they satisfy all other enrollment criteria and are willing to convert to MDI for the duration of the study, beginning 6 weeks prior to enrollment. They must continue to meet all enrollment criteria after converting to the MDI regimen;
 
7. Total daily insulin dose ≤ 1.5 units/kg/day with a minimum of 3 units of RAA at every meal.
 
8. Hemoglobin A1c (HbA1c) 7.0% to 10.0% at the time of screening;
 
9. Fasting serum C-peptide ≤ 0.3 ng/mL;
 
10. Forced expiratory volume in 1 second (FEV₁) $\geq 70\%$ of National Health and Nutrition Examination Survey (NHANES) III predicted for children ≥ 8 years of age or Wang predicted for children < 8 years of age;
 
11. Forced vital capacity $\geq 70\%$ of NHANES III predicted for children ≥ 8 years of age or Wang predicted for children < 8 years of age;
 
12. Subjects of childbearing potential must use “highly effective” methods of contraception. These include, for example, a state after surgical sterilization, hormonal intrauterine devices (coil), oral hormonal contraceptives, sexual abstinence or a surgically sterilized partner. “Highly effective” methods are considered those with a low failure rate (i.e., less than 1% undesired pregnancies per year). During the entire trial females of childbearing potential

--	---

	
must use two contraceptive methods which are independent from each other, e.g. an intrauterine contraceptive coil or oral hormonal contraceptive plus a vaginal diaphragm or a condom coated with a spermicidal substance. The use of a condom in combination with spermicidal creams, however, is not sufficiently reliable.
 
Exclusion criteria:
 
1. Body mass index below 25th or above 95th percentile for age and gender according to Centers for Disease Control and Prevention growth charts: https://www.cdc.gov/growthcharts/html_charts/bmiagerev.htm2. History of physician diagnosis of asthma or any other clinically important pulmonary disease, or use of any medications to treat such conditions within the last year;3. Allergy or known hypersensitivity for AFREZZA or to drugs with similar chemical structure;4. Unstable diabetes control, defined as 2 or more episodes of severe hypoglycemia (i.e., an episode associated with a seizure, coma, or loss of consciousness) or any hospitalization or emergency room visit for poor diabetes control, ketoacidosis, hypoglycemia, or hyperglycemia within the preceding 3 months from screening;5. Serum creatinine \geq the upper limit of normal for age;6. Respiratory tract infection within 30 days before screening or between screening and initiation of treatment period; subject may return 4 weeks after resolution of the infection for rescreening;7. Evidence of any complication of diabetes (proliferative retinopathy, autonomic neuropathy, nephropathy, etc), or likelihood of requiring laser photocoagulation, vitrectomy, or other specific treatment for diabetic retinopathy in the coming year;8. Smoking of tobacco or other substances or positive urine cotinine testing (>100 ng/mL);9. Positive urine drug screen;10. Positive urine pregnancy test for female subjects of childbearing potential;11. Inability to perform study procedures including pulmonary function testing;
--	---

	
12. Exposure to any investigational product(s) in the past 3 months or 5 half-lives, whichever is more;
 
13. History of eating disorder;
 
14. Any disease or exposure to any medication which, in the judgment of the principal Investigator, may impact glucose metabolism;
 
15. Any concurrent medical or major psychiatric condition that makes the subject unsuitable for the clinical study or impairs the subject's ability to participate in the study.

Total expected number of subjects	Approximately 46 subjects will be enrolled in the Part 1 of the study (18 subjects for 13 to 17-year-old cohort, 14 subjects for 8 to 12-year-old cohort, and 14 subjects for 4 to 7-year-old cohort).
STUDY TREATMENTS	
Investigational medicinal product	AFREZZA® (insulin human) Inhalation Powder and Inhaler
Formulation	
Recombinant DNA origin
 
Each milligram of formulation contains 3.0 units of human insulin

Route of administration	Inhalation
Dose regimen	At the beginning of each meal
Non-investigational medicinal product	Basal insulin (e.g., insulin glargine)
Formulation	Long acting insulin analog
Route of administration	Subcutaneous injection
Dose regimen	Daily dose as instructed by Physician
ENDPOINTS	
Pharmacokinetic endpoints
 
 • Insulin C_{max} (maximum observed concentration after correction for baseline) • Insulin $AUC_{0-tlast}$ (area under the baseline-corrected concentration-time curve from time 0 to the last measurable concentration) • Insulin t_{max} (time to C_{max}) • Insulin apparent clearance (CL/F) • Insulin apparent volume of distribution (V_{ss}/F) • Fumaryl diketopiperazine (FDKP) elimination half-life ($t_{1/2}$) • Insulin AUC (area under the serum concentration versus

	
time curve extrapolated to infinity according to the following equation:
 $AUC = AUC_{last} + C_{last}/\lambda_z$ 
Safety endpoints:
 
 • Adverse events, serious adverse events, treatment-emergent adverse events • Adverse Events of Special Interest (AESI), which include the following events: 
 • Acute bronchospasm • Clinically relevant decline in pulmonary function • Hypersensitivity reactions, including anaphylaxis, which can occur with insulin products, including AFREZZA® • Diabetic ketoacidosis • Vital sign measurements • Abnormal clinical laboratory assessments • Hypoglycemia: asymptomatic, symptomatic, nocturnal, and severe hypoglycemia according to the 2014 International Society for Pediatric and Adolescent Diabetes guideline • Anti-insulin antibodies
ASSESSMENT SCHEDULE	The schedule of study-related procedures/assessments is detailed in the study flow chart.
STATISTICAL CONSIDERATIONS	
Sample size determination:
 
Sample size calculation is based on a total standard deviation (SD_{Total}) of 0.725 for the log-transformed apparent total body clearance (CL/F). The sample size is planned to target the maximum imprecision of the 95% confidence interval for the geometric mean estimates of CL/F in each age cohort within 40%, with at least 80% power.
 
A sample size of 14 subjects in the first cohort will provide at least 80% power in order to target the maximum imprecision of the 95% confidence interval of the geometric mean estimates within 40%, assuming an SD_{Total} of 0.725 as the most conservative approach. For Cohort 2 and Cohort 3, the sample size may be adjusted to enable taking the PK variability in previous cohorts into account.
 
Analysis population:
 
All subjects in the clinical study who receive a dose of

	
AFREZZA will be included in the safety population.
 
All subjects without any major deviations related to study drug administration (no sneezing or coughing right after AFREZZA inhalation on Day 1), and for whom any PK parameters are available, will be included in the PK population.
 
Pharmacokinetic analysis:
 
All analyses will be performed in a descriptive manner based on the PK population.
 
Safety analyses:
 
Analyses will be performed in a descriptive manner by age cohort.
 
The safety analysis will be conducted on the safety population and will be based on the review of the individual values (clinically significant abnormalities) and descriptive statistics (summary tables and plots if appropriate). Individual values will be flagged for potentially clinically significant abnormalities and treatment-emergent adverse events will be tabulated (counts and percent). The details of the analyses for the study will be specified in the Statistics and Analysis Plan (SAP) for the study.

DURATION OF STUDY PERIOD (per subject)	The total duration of the study will be approximately 6 to 8 weeks per subject through the 4-week titration period.
STUDY COMMITTEES	Data Monitoring Committee: an independent group of experts will be responsible for monitoring the safety of the subjects enrolled in the clinical trial on an on-going basis in order to provide, in a timely fashion, appropriate recommendations to the Sponsor.

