7.2 INCLUSION CRITERIA

Eligible subjects must meet all the following inclusion criteria for Part 1 of the study:

1. Written or oral assent from the pediatric subject and written informed consent from the parent(s) or legal guardian and a witness, as required by both state and federal laws and the local Institutional Review Board;
2. Children aged ≥ 4 and ≤ 17 years (enrolled into 3 age cohorts: 13 to 17, 8 to 12, and 4 to 7 years);
3. Clinical diagnosis of T1DM and using insulin for at least 1 year;
4. Currently receiving a regimen of basal/bolus insulin administered by MDI for at least 6 weeks prior to enrollment.
5. Subjects with pre-breakfast SMBG values between 80 and 250 mg/dL for 5 of 7 documented daily readings obtained in the week prior to Visit 2 (reading to be taken using glucometer provided at Screening Visit 1) and reported via the e-Diary;
6. Subjects on a regimen of insulin via continuous SC insulin infusion may be enrolled if they satisfy all other enrollment criteria and are willing to convert to MDI for the duration of the study, beginning 6 weeks prior to enrollment. They must continue to meet all enrollment criteria after converting to the MDI regimen;
7. Total daily insulin dose ≤ 1.5 units/kg/day with a minimum of 3 units of RAA at every meal.
8. HbA1c 7.0% to 10.0% at the time of screening;
9. Fasting serum C-peptide ≤ 0.3 ng/mL;
10. Forced expiratory volume in 1 second (FEV₁) $\geq 70\%$ of National Health and Nutrition Examination Survey (NHANES) III predicted for children ≥ 8 years of age or Wang predicted for children < 8 years of age (8), (9);
11. Forced vital capacity $\geq 70\%$ of NHANES III predicted for children ≥ 8 years of age or Wang predicted for children < 8 years of age (8), (9);
12. Subjects of childbearing potential must use “highly effective” methods of contraception. These include, for example, a state after surgical sterilization, hormonal intrauterine devices (coil), oral hormonal contraceptives, sexual abstinence or a surgically sterilized partner.

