9.2.3 Screening assessment

Informed Consent/Accent will be obtained prior to performing any screening procedures. The safety assessment at screening will be performed according to the Flow Chart 1.1 and will include:

- Assessment of inclusion and exclusion criteria
- Physical examination (at screening): full physical examination, including ear, nose, throat, lung and cardiac auscultation, recording of Tanner stages of pubertal development and excluding genitourinary and rectal examinations
- Oral body temperature, body weight, and height
- Vital signs (respiratory rate, sitting blood pressure, and pulse measurements) will be recorded with the subject in a sitting position for 5 minutes before the measurement is taken.
- HbA1c

- Fasting serum C-peptide
- Laboratory tests:
 - Serology tests: hepatitis B antigen, hepatitis C antibodies, anti-HIV-1 and anti-HIV-2 antibodies
 - Anti-Insulin Antibody
 - Pregnancy test: females of childbearing potential
 - Urine cotinine
 - Urine drug screening: amphetamines/methamphetamines, barbiturates, benzodiazepines, cannabinoids, cocaine, and opiates
 - Alcohol breath or plasma test
 - Hematology: red blood cell count, hematocrit, hemoglobin, white blood cell count with differential count (neutrophils, eosinophils, basophils, monocytes, and lymphocytes), platelets
 - Biochemistry:
 1. Plasma/serum electrolytes: sodium, potassium, chloride, calcium, phosphorus, carbon dioxide
 2. Liver function: aspartate aminotransferase, alanine transaminase, alkaline phosphatase, total and conjugated bilirubin
 3. Renal function: blood urea nitrogen, creatinine, uric acid
 4. Metabolism: albumin, total proteins, total cholesterol, low-density lipoprotein, triglycerides
 5. Potential muscle toxicity: creatinine phosphokinase, lactate dehydrogenase
 - Urinalysis: albumin/creatinine ratio, ketones, glucose, erythrocytes, and leucocytes count, pH, urobilinogen, nitrates, specific gravity
- A standard 12-lead electrocardiogram recorded after at least 10 minutes in a supine position
- FEV₁ testing: Spirometry (FEV₁) will be done to assess pulmonary function. Another pulmonary function test may be done after consultation with a pediatric pulmonologist if the subject is unable to perform spirometry
- Adverse events (AEs) spontaneously reported by the subject or observed by the Investigator will be monitored
- Prior/concomitant medications reported by the subject or by the Investigator will be

recorded

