12.1.3.4 End of titration (Visit 15)

Subjects will return to the site 3 ± 1 days after the last telephone contact at Visit 14. During this visit (Visit 15), FEV₁ will be assessed, and post-dose SMBG values since the last visit and current AFREZZA® doses will be reviewed. Subjects will be discharged from the clinic after an abbreviated physical examination (evaluating general appearance, mental status, respiratory and cardiovascular systems, and any other evaluations deemed necessary by Investigator).

Subjects will be assessed according to the Flow Chart [1.1](#). Assessments include but are not limited to the following:

- Urine pregnancy test for females of childbearing potential
- HbA1c
- Urine cotinine
- Anti-insulin antibody
- Review of concomitant medications and AEs
- Abbreviated physical examination (general appearance, mental status, respiratory and cardiovascular systems, and other evaluations deemed appropriate by the Investigator for safety reasons)
- Body weight
- Vital sign measurements
- Blood glucose via glucose meter reading
- Spirometry or another pulmonary function test for a subject who is unable to perform the spirometry test
- 7-point glucose data will be reviewed
- Subjects will return all study supplies and receive a prescription for usual prandial RAA and for basal insulin

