8.3.5 Pulmonary Function Testing

Schedule and parameters

Spirometry tests will be performed at screening, visits 2, 9, 15, and 16 in the titration period, visits 19, 22, 25, 28, and 29 in the extension period, as well as at the early termination visits in both periods. At each visit, Forced Expiratory Volume in 1 second (FEV₁) will be collected. At Visit 2, FEV₁ will be collected at several time points: -25 min, 18 min, 55 min, 125 min and 245 min relative to the time of first dose.

Table presentation

FEV₁ value and change from baseline will be summarized descriptively by cohort and analysis visit/nominal time point. For each post-baseline visit/time point, number and percentage of subjects with verified clinically relevant decline in pulmonary function from baseline (as indicated on the eCRF) will be presented by cohort. For percentage calculations, the total number of subjects in each cohort who attend the visit will be used as denominators.

Verified clinically relevant decline in pulmonary function will be captured as AE. A continuous decline will be captured as a single AE. The start date of this event is defined as the date when the criterion of clinically relevant decline (i.e., >15% decrease from baseline) is met for the first time, and the end date of this event is defined as the date when the criterion is no longer met. Each event will be assigned to a study period based on the start date. Duration (in days) of an event will be calculated as end date – start date + 1, and summarized by cohort and study period.

Subject Listings

For spirometry tests, detailed information of every measurement will be listed, by (in the order of) cohort, investigator site, subject and visit/time point.

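### Protocol 9.2.3 allows a non-spirometric test at screening without saying whether it can meet the FEV1 and FVC entry criteria, and the SAP decline percentage would count a dosed child who has no FEV1 baseline

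*Protocol*

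**What the plan says.** **Entry.** Protocol 7.2 opens with "Eligible subjects must meet all the following inclusion criteria for Part 1 of the study". Criteria 10 and 11 then set FEV1 and FVC at 70% of predicted or more, using one reference equation from age 8 and another below it. Table 1 in section 4.4 gives the same thresholds as the entry safeguard against the FEV1-decline risk. Section 12.1.1 repeats that all inclusion criteria and none of the exclusion criteria must be satisfied. Exclusion criterion 11 (7.3 and the Clinical Study Summary) removes a child for "Inability to perform study procedures including pulmonary function testing".

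**Screening test.** Section 9.2.3, on FEV1 testing at screening, adds: "Another pulmonary function test may be done after consultation with a pediatric pulmonologist if the subject is unable to perform spirometry". Section 9.2.4 makes almost the same allowance for testing during the study. Visits 15 and 16 (12.1.3.4 and 12.1.3.5) list "Spirometry or another pulmonary function test for a subject who is unable to perform the spirometry test". The flow chart in 1.1 and the early termination list in 12.1.4 name spirometry only.

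**Analysis.** SAP 8.3.5 names one lung-function variable: "At each visit, Forced Expiratory Volume in 1 second". Decline means a fall of more than 15% from baseline, and the percentage is taken over all subjects in the cohort who attend the visit. SAP 5.2 defines baseline as the last pre-dose measurement on or before Study Day 1.

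**Infection.** Exclusion 6 bars a respiratory tract infection within 30 days before screening and continues: "subject may return 4 weeks after resolution of the infection for rescreening".

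**The concern.** The sentence in 9.2.3 stands in the screening section, and on-study testing has its own sentence in 9.2.4. So it cannot be read as flexibility for later visits. At screening it either has no effect on eligibility, because criteria 10 and 11 still need a spirometric value, or it lets a child qualify on another test. The protocol does not say which. Two sites could each follow a protocol passage and decide differently about the same child.

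Clinically relevant decline in pulmonary function is an adverse event of special interest. Section 4.4 states that safety has not been evaluated in children, and section 4.2 says the data will help set the age range for Part 2. The FEV1 and decline tables are in the DMC package (SAP Appendix 3). A child dosed without an FEV1 baseline would enter the decline percentage only as a non-event, which makes the percentage look more favourable than the data support. An alternative-test result has no planned table, and the listing in 8.3.5 covers spirometry only.

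**Working it through.** The plan states no figure on this point, so there is none to reproduce. The check compares the texts and then does simple arithmetic.

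**Step 1. Can 9.2.3 be squared with 7.2?**

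| Place | What it requires or allows | Alternative to spirometry? |
|---|---|---|
| 7.2, criteria 10 and 11 | FEV1 and FVC at least 70% of predicted | None named |
| 7.3, exclusion 11 | Must be able to do pulmonary function testing | Term wider than spirometry |
| 9.2.3, screening | Another test if unable to do spirometry | Yes; no test, threshold or link to criteria 10 and 11 |
| 9.2.4, Visits 15 and 16 | Another test on study | Yes |
| 12.1.2, Visit 2 before dosing | FEV1 by spirometry | None named |

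An alternative test yields no FEV1 or FVC to compare with 70% of predicted. Under 7.2 alone the child is not eligible. Section 9.2.3 leaves open whether the other test may stand in.

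**Step 2. What happens in the SAP if such a child is dosed?** FEV1 is scheduled 1 (screening) + 5 (Day 1) + 3 (Visits 9, 15 and 16) = 9 times. Two of these precede dosing: screening and the -25 minute test on Day 1. If the Day 1 pre-dose test succeeds, it is a valid baseline under SAP 5.2. If both fail, change from baseline and the >15% criterion are undefined, while the child still counts as attending.

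**Step 3. Size of the denominator effect.** Inputs: a cohort of 14 (protocol 7.1) and *k* children without an FEV1 baseline. The documents give no value for *k*; 1 to 4 is assumed. It is also assumed that all 14 attend the visit and that every child with a baseline has an FEV1 there.

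- Reported for one decline: 1/14 = 7.1%.
- Among evaluable children: 1/(14 - *k*).
- With no declines, the exact one-sided 95% upper bound on *n* children is 1 - 0.05^(1/*n*). The SAP does not plan this bound; it is shown only to gauge the information lost.

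| *k* | Evaluable | One decline, reported | One decline, evaluable | Upper bound at zero, *n* = 14 | Upper bound at zero, evaluable |
|---|---|---|---|---|---|
| 1 | 13 | 7.1% | 7.7% | 19.3% | 20.6% |
| 2 | 12 | 7.1% | 8.3% | 19.3% | 22.1% |
| 3 | 11 | 7.1% | 9.1% | 19.3% | 23.8% |
| 4 | 10 | 7.1% | 10.0% | 19.3% | 25.9% |

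**Step 4. Infection intervals.** 4 weeks = 4 x 7 = 28 days, and 30 - 28 = 2 days. If the 30 days cover any day of illness up to resolution, a child returning on day 28 or 29 after resolution still meets the exclusion (day 30 as well if the limit is inclusive). If they run from onset and the illness lasted *L* days, a child returning at day 28 is 28 + *L* days from onset. The clash then exists only for *L* below 2, or up to 2 if inclusive.

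**The case against.** The best defence is that the protocol already bars entry without spirometry. Sections 4.4, 7.2 and 12.1.1 each require the thresholds or all the criteria, the criteria are reviewed again at Visit 2, and pre-dose spirometry is listed there. Section 9.2.3 is a list of assessments. It says that another test may be done, not that the result confers eligibility. A child enrolled that way could be handled as a protocol deviation under SAP 8.1.2. This stands as a strict reading, and it makes the consequence conditional. It does not explain what the screening sentence is for.

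Several stronger readings are tempting, but the documents do not support them:

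- *Exclusion 11 contradicts 9.2.3.* A child who manages another lung-function test need not meet exclusion 11. The tension is with inclusion criteria 10 and 11.
- *Visits 15 and 16 show that children unable to do spirometry are enrolled.* That text equally fits a child who qualified and later could not perform.
- *Decline could never be assessed in such a child.* A successful Day 1 pre-dose test supplies the baseline. Investigators can also report decline in pulmonary function as an event of special interest, which the protocol does not tie to FEV1.
- *The problem falls mainly on ages 4 to 7.* This is plausible, but the documents do not say so.
- *Exclusion 6 readmits a child at 28 days.* It permits return for rescreening, where every criterion applies again.

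**Conclusion.** The point holds as an unresolved inconsistency between 7.2 and 9.2.3, together with an SAP denominator that does not allow for a missing FEV1 baseline. It does not show that the plan admits children without spirometry. Harm requires three things: a site relies on 9.2.3, the child is dosed, and the Day 1 pre-dose spirometry also fails.

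Under the assumption of 1 to 4 such children in a cohort of 14, one decline would be reported as 7.1% instead of 7.7% to 10.0% of those evaluable. The number affected is unknown and may be zero. The effect is on a descriptive safety summary and has no bearing on the sample size. It still merits correction, because the bias is toward reassurance on a lung-safety endpoint and the remedy is small.

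The infection intervals are a minor wording inconsistency of 2 days, dependent on a starting point that the protocol does not define.

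**What to change.** 1. **Protocol.** Reconcile 7.2, 7.3 and 9.2.3 with 9.2.4 and Visits 15 and 16. State whether a spirometric FEV1 and FVC must be on record before dosing. If the sponsor intends another test to count, name it, give its threshold and say which criteria it satisfies. The eligibility rule is for the sponsor to choose.
2. **SAP 8.3.5.** For the decline percentage, use as denominator the subjects with both a baseline FEV1 and a post-baseline FEV1 at that visit. Show the number attending beside it, and list any alternative-test results.
3. **Exclusion 6.** Reconcile the 30-day and 4-week intervals and state when the 30-day count starts.

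The cost is wording, plus a small change to one table and one listing. If spirometry before dosing is confirmed as mandatory, a few children who cannot perform it will not be enrolled, which criteria 10 and 11 already imply.
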